Table LAHB.2.	Treatments Administered.....	25

List of Figures

Figure	List of Figures	Page
Figure LAHB.1.	Illustration of study design for Protocol H8H-MC-LAHB.....	16

List of Appendices

Appendix		Page
Appendix 1.	Abbreviations and Definitions	44
Appendix 2.	Clinical Laboratory Tests.....	49
Appendix 3.	Study Governance, Regulatory, and Ethical Considerations	50
Appendix 4.	Hepatic Monitoring Tests for Treatment-Emergent Abnormality	53
Appendix 5.	Blood Sampling Summary.....	54
Appendix 6.	Protocol Amendment H8H-MC-LAHB(c) Summary: A Randomized, Subject- and Investigator-Blind, Placebo- and Active-Controlled Study to Assess the Abuse Potential of Lasmiditan.....	55

1. Protocol Synopsis

Title of Study:

A Randomized, Subject- and Investigator-Blind, Placebo- and Active-Controlled Study to Assess the Abuse Potential of Lasmiditan

Rationale:

Lasmiditan is being developed for the acute treatment of migraine. Because lasmiditan penetrates the central nervous system and adverse events possibly related to abuse have been reported in completed clinical studies, the risk of abuse should be evaluated in accordance with the United States Food and Drug Administration's Guidance for Industry: Assessment of Abuse Potential of Drugs (2017).

Objective(s)/Endpoints:

Objectives	Endpoints
Primary To assess the abuse potential of lasmiditan compared to the positive control alprazolam and placebo	The difference in the maximal effect score (E_{max}) during the 24 hours after dosing of the at-the-moment 100-mm bipolar Drug Liking Visual Analog Scale (VAS) scores for: 
 • alprazolam versus placebo • lasmiditan versus alprazolam • lasmiditan versus placebo
Secondary 
 • Further characterize the abuse potential of lasmiditan with additional Drug Effects and Drug Similarity VAS measures • Safety evaluations • Pharmacokinetics of lasmiditan 	
 • Assessing additional Drug Effects and Drug Similarity VAS measures in addition to the time course of the assessments: overall drug liking, take drug again, any effects, good effects, bad effects, alertness/drowsiness, agitation/relaxation, high, hallucination, and similarity. • Treatment-emergent adverse event profiles • Pharmacokinetic parameters: area under the concentration versus time curve (AUC) and maximum observed drug concentration (C_{max})

Summary of Study Design:

Study H8H-MC-LAHB is a Phase 1, randomized, subject- and investigator-blind, placebo- and active-controlled, crossover clinical trial in adult subjects who are recreational poly-drug users. This study includes 4 phases:

Screening Phase: A screening phase will determine the eligibility of subjects for the study based on the results of screening medical history, physical examination, vital signs, clinical laboratory tests, and electrocardiogram (ECG). Subjects who meet the screening criteria will enter the Qualification Phase.

Qualification Phase: This will be a subject- and investigator-blind, placebo-controlled, 2-period crossover study designed to identify subjects who are able to discriminate an alprazolam test dose from placebo. Only subjects who meet alprazolam qualification criteria will be eligible to enter the Treatment Phase.

Treatment Phase: This will be a subject- and investigator-blind, placebo- and active-controlled, 5-period crossover study to evaluate the abuse potential of placebo, alprazolam, and 100-mg, 200-mg, and 400-mg lasmiditan.

Follow-up Phase: Subjects will enter a follow-up phase after their last dose of study drug.

Treatment Arms and Planned Duration for an Individual Subject:

For the Qualification Phase, subjects will be randomized to a test dose of 1-mg alprazolam and placebo in a crossover manner with a washout period of at least 3 days (72 hours) between each dose.

For the Treatment Phase, subjects will be randomized to 1 of 10 dosing sequences; each dosing sequence consists of 5 dosing periods that evaluate the abuse potential of 1 of the 5 study treatments: placebo, 2-mg alprazolam, 100-mg lasmiditan, 200-mg lasmiditan, and 400-mg lasmiditan. The washout period between each dose of at least 3 days (72 hours). A follow-up visit will occur approximately 1 week after the last dose of study drug.

Number of Subjects:

An appropriate number of subjects will be screened to allow for approximately 130 subjects to enter into the Qualification Phase so that approximately 60 subjects are randomized in the Treatment Phase and approximately 50 subjects complete the study. Subjects will be randomly assigned to 1 of 10 treatment sequences, determined by the repeated Williams square design. This will lead to 90% or more power for testing each of the hypotheses of primary interest regarding the Drug Liking Visual Analog Scale (VAS) endpoints.

Statistical Analysis:

Subjects who complete all 5 periods of the Treatment Phase will comprise the completers population; this will be the population used for analyzing the Drug Effects VAS Battery. Descriptive statistics for continuous variables will include mean, standard error, minimum, first quartile, median, third quartile, and maximum. Descriptive statistics for categorical variables include count and percent.

Descriptive statistics for the Drug Liking VAS will be reported for each treatment and for each paired difference among treatments. A linear mixed-effects model, which includes period, sequence, and treatment as fixed effects, and subject as a random effect will be used to evaluate the hypothesis tests of primary interest at the peak of drug response effects (E_{max}) at a significance level of 0.05 (1-sided).

Descriptive statistics for other measures in the Drug Effects and Drug Similarity VAS Battery, adverse events, safety laboratory parameters, vital signs, Columbia-Suicide Severity Rating Scale (C-SSRS), ECG, and pharmacokinetic parameters will be reported by treatment.

2. Schedule of Activities

2.1. Qualification Phase

Study Schedule Protocol H8H-MC-LAHB: Qualification Phase

Procedure	Screening Phase	Qualification Phase: Periods 1-2				Comment
Study Day	-28 to -2	-1	1	2	D/C or ET	Minimum of 3 days = 72 h washout between doses
Informed Consent	X					
Visits	O	I	I	I	O	I: inpatient; O: outpatient
Medical History	X					
Drug History	X					
Height	X					
Weight	X	X			X	Weight will be collected at screening, Qualification Phase Period 1, and D/C or ET.
ECG	X	X				
Screening Labs	X					
Study Drug Dosing			X			Study drug will be administered on Day 1 after an overnight fast.
AE/Medication Review	X	X	X	X	X	
PE	X	X				Full PE at screening and first CRU admission. Symptom-driven PE at all other time points as deemed necessary by PI.
BP/Pulse	X	X	0, 1, 2, 4, 6	24	X	Single supine BP and pulse rate.
Urine Drug Screen and Alcohol Screen	X	X				Urine Drug and Alcohol screen will be collected at screening and Qualification Phase Period 1 (additional test may be performed at Period 2 if subject discharged between periods).
Pregnancy Test	X	X				Serum test at screening. Serum or urine tests thereafter. Pregnancy test will be collected at screening and Qualification Phase Period 1 (additional test will be performed at Period 2 if subject discharged between periods).
CBC and Chemistry	X	X			X	Performed as a fasting sample on Day -1 of Period 1 only.
VAS training		X				VAS training to occur on Day -1 of each Period
Drug Effects VAS Battery			0, 0.25, 0.5, 1, 1.5, 2, 2.5, 3, 3.5, 4, 4.5, 5, 6, 8, 12	24		Overall Drug Liking and Take Drug Again assessed at 12 and 24 hours postdose only.
Drug Similarity VAS Battery				24		Drug Familiarity VAS, a subset of Drug Similarity VAS, will be administered at Day 2 Qualification Phase Period 1 only.
C-SSRS/Self Harm	X	X			X	A self-harm form may be administered at time of C-SSRS. C-SSRS/Self Harm will be administered at screening, Day -1 Qualification Phase of Period 1, and D/C or ET (additional test will be performed at Period 2 if subject was discharged between periods).

Abbreviations: AE = adverse event; BP = blood pressure; CBC = complete blood counts; CRU = clinical research unit; C-SSRS = Columbia-Suicide Severity Rating Scale; D/C = discontinuation; ECG = electrocardiogram; ET = early termination; h = hour; labs = laboratory tests; mins = minutes; PE = physical examination; PI = principle investigator; VAS = visual analogue scale.

Note: if multiple procedures take place at the same time point, the following order of the procedure should be used: ECG, vital signs, and venipuncture.

^a Should be taken in the following order: ECG ± 15 mins, BP/Pulse ± 15 mins, and VAS ± 15 mins at nominal time point.

2.2. Treatment Phase

Study Schedule Protocol H8H-MC-LAHB: Treatment Phase

Procedure	Treatment Phase: Periods 1-5				Follow-up Phase	Comment
Study Day	-1	1	2	D/C or ET	20	Minimum of 3 days = 72 h washout between doses
Visits	I	I	I		O	I: inpatient; O: outpatient; Follow-up = approximately 1 week after last dose of study drug.
Weight	X			X	X	Weight will be collected at Treatment Phase Period 1, D/C or ET, and Follow-up.
ECG	X	0, 2, 4	24	X	X	
Study Drug Dosing		X				Study drug will be administered on Day 1 after an overnight fast.
AE/Medication Review	X	X	X	X	X	
PE	X					Full PE at first CRU admission. Symptom-driven PE at all other time points as deemed necessary by PI.
BP/Pulse	X	0, 1, 2, 4, 6	24	X	X	Single supine BP and pulse rate. Follow same window as PK.
Urine Drug Screen and Alcohol Screen	X				X	Urine Drug and Alcohol screen will be collected at Treatment Phase Period 1 and Follow-up (additional test will be performed at Periods 2-5 if subject discharged between periods).
Pregnancy Test	X				X	Pregnancy test will be collected at Treatment Phase Period 1 only and Follow-up (additional test will be performed at Periods 2-5 if subject discharged between periods).
CBC and Chemistry	X				X	Fasting samples on Days -1 of all periods.
VAS training	X					VAS training to occur on Day -1 of each Period
Drug Effects Battery		0, 0.25, 0.5, 1, 1.5, 2, 2.5, 3, 3.5, 4, 4.5, 5, 6, 8, 12	24			Overall Drug Liking and Take Drug Again assessed at 12 and 24 hours postdose only.
Drug Similarity VAS Battery			24			
C-SSRS/ Self-Harm	X			X	X	A self-harm form may be administered at time of C-SSRS. C-SSRS/Self Harm will be administered on Day -1 Treatment Phase Period 1, D/C or ET, and Follow-up (additional test will be performed at Periods 2-5 if subject discharged between periods).
PK		0, 0.5, 1, 1.5, 2, 2.5, 3, 4, 6, 8, 12	24			
Genetic Sample	X					Genetic samples will be collected at the first period of Treatment Phase only.

Abbreviations: AE = adverse event; BP = blood pressure; CBC = complete blood counts; CRU = clinical research unit; C-SSRS = Columbia-Suicide Severity Rating Scale; D/C = discontinuation; ECG = electrocardiogram; ET = early termination; h = hour; PE = physical examination; PI = principle investigator; PK = pharmacokinetics; VAS = visual analogue scale.

Note: if multiple procedures take place at the same time point, the following order of the procedure should be used: ECG, vital signs, and venipuncture.

^a Should be taken in the following order: ECG \pm 15 mins, BP/Pulse \pm 15 mins, PK \pm 5 mins, and VAS \pm 15 mins at nominal time point.

3. Introduction

3.1. Study Rationale

Lasmiditan is a centrally penetrant, potent, and selective small-molecule 5-hydroxytryptamine (5-HT)_{1F} receptor agonist. Lasmiditan is being developed by Eli Lilly and Company (Lilly) for the acute treatment of migraine. This molecule has been developed by Lilly as LY573144 and by CoLucid Pharmaceuticals, Inc. (CoLucid) as COL-144.

Because lasmiditan penetrates the central nervous system (CNS) and adverse events (AEs) possibly related to abuse have been reported in completed clinical studies, the risk of abuse will be evaluated in accordance with the United States (US) Food and Drug Administration's (FDA's) Guidance for Industry: Assessment of Abuse Potential of Drugs (FDA 2017).

3.2. Background

Two Phase 2 studies have been completed with lasmiditan in the acute treatment of migraine, using intravenous (IV) and tablet formulations, respectively. One Phase 3 randomized, double-blind, placebo-controlled trial has been completed in the US (COL MIG-301 [SAMURAI]). In the SAMURAI study, both 100- and 200-mg doses of orally administered lasmiditan achieved superior 2-hour pain-free rate and a relief for the most bothersome migraine symptoms compared to baseline.

Five Phase 1 studies of lasmiditan have been completed using IV, sublingual, and oral formulations of lasmiditan in healthy subjects. Single doses of lasmiditan up to 400 mg were tolerated by healthy subjects.

In healthy subjects, peak plasma concentrations of lasmiditan were observed approximately 1 hour to 2.5 hours after a single oral dose, and the geometric mean terminal half-life was approximately 4 to 6 hours. Lasmiditan exhibited dose-linear pharmacokinetics (PK); low to moderate intersubject variability in exposure was observed across doses (percent coefficient of variation [%CV] up to 61% and 45% for maximum observed drug concentration [C_{max}] and area under the curve [AUC], respectively. Renal clearance of lasmiditan was low, with approximately 2% of the parent dose recovered by 24 hours postdose. Coadministration of lasmiditan with a high fat diet led to a delay in median time to maximum concentration (T_{max}) value by approximately 1 hour and a modest (approximately 20%) increase in C_{max} and AUC values, relative to that under fasted conditions.

Based on the currently available data from in vitro and in vivo studies in humans, lasmiditan appears to be eliminated primarily through both non-cytochrome P450 (CYP) and CYP-mediated metabolism to form metabolites M8 (keto-reduced metabolite), M7 (carbonyl oxidized metabolite), and M18 (keto-reduced, carbonyl oxidized metabolite). All 3 of these major metabolites circulate in humans are not considered to be active, and have been quantitated in pharmacokinetic (PK) studies.

Across the completed Phase 1, 2, and 3 clinical studies, doses of 0.1 to 400 mg of lasmiditan were evaluated in healthy subjects or patients with migraine; methods of administration included

IV, oral, and sublingual. Compared with placebo, the most frequently reported treatment-emergent adverse events (TEAEs) that could possibly indicate abuse potential after receiving lasmiditan included somnolence, fatigue, dizziness, and hot flash. Less frequently reported TEAEs possibly related to abuse after receiving lasmiditan included euphoric mood, hallucination, and feeling abnormal. A majority of these TEAEs were mild or moderate in severity and none led to subjects' withdrawal. One subject experienced a serious adverse event (SAE) of dizziness that was moderate in severity (lasmiditan 200 mg; COL-MIG 202).

Nonclinical receptor-binding results indicated that with the exception of the 5-HT_{1F} receptor subtype, lasmiditan and its major metabolites (M7, M8, and M18) do not demonstrate affinity for 5-HT₁ serotonin receptor subtypes. Lasmiditan also had poor affinity for the benzodiazepine binding site on the gamma-aminobutyric acid (GABA)_A ionophore. Additionally, in a rat drug discrimination study, in which lorazepam served as a positive control, none of the lasmiditan doses tested (10, 30, and 100 mg/kg) produced a discriminative stimulus similar to lorazepam.

3.3. Benefit–Risk Assessment

This study compares the abuse potential for lasmiditan versus placebo, and versus alprazolam in experienced recreational polydrug users. Thus, there is no anticipated therapeutic benefit for the subjects in this study.

To date, lasmiditan has been tolerated by healthy subjects after single dose oral administration up to 400 mg. The most frequently reported AEs in clinical studies include somnolence, dizziness, fatigue, and hot flash. More information about the known and expected benefits, risks, SAEs, and reasonably anticipated AEs of lasmiditan are to be found in the Investigator's Brochure (IB).

Alprazolam, a short-acting benzodiazepine, has been chosen as a positive control. Potential risks from alprazolam include sedation and somnolence. Administration of lasmiditan and alprazolam will be conducted in inpatient setting, with monitoring of adverse reactions, vital signs, and electrocardiograms (ECGs). Adverse events will be managed with supportive care.

Only subjects with a prior history of recreational drug use will be enrolled in this study and a maximum of 2 doses within the therapeutic dose range of alprazolam will be administered to minimize potential risks, including the risk for dependence. Subjects at risk of adverse reaction from alprazolam, including subjects with a prior history of benzodiazepine dependence, seizures, or depression and concomitant use of CYP3A inhibitors will be excluded from the study.

Information about known risks for alprazolam can be found in the package insert for alprazolam.

4. Objectives and Endpoints

Table LAHB.1 shows the objectives and endpoints of the study.

Table LAHB.1. Objectives and Endpoints

Objectives	Endpoints
Primary To assess the abuse potential of lasmiditan compared to the positive control alprazolam and placebo	The difference in the maximal effect score (E_{max}) during the 24 hours after dosing of the at-the-moment 100-mm bipolar Drug Liking Visual Analog Scale (VAS) scores for: 
 • alprazolam versus placebo • lasmiditan versus alprazolam • lasmiditan versus placebo
Secondary 
 • Further characterize the abuse potential of lasmiditan with additional Drug Effects and Drug Similarity VAS measures • Safety evaluations • Pharmacokinetics of lasmiditan 	
 • Assessing additional drug effects and drug similarity VAS measures in addition to the time course of the assessments: overall drug liking, take drug again, any effects, good effects, bad effects, alertness/drowsiness, agitation/relaxation, high, hallucination, and similarity. • Treatment-emergent adverse event profiles • Pharmacokinetic parameters: area under the concentration versus time curve (AUC) and maximum observed drug concentration (C_{max})
Tertiary/Exploratory Pharmacokinetics of alprazolam	
 • Pharmacokinetic parameters: AUC and C_{max}

5. Study Design

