5.1. Overall Design

This study is a Phase 1, randomized, subject- and investigator-blind, placebo- and active-controlled, crossover clinical trial in adult subjects who are recreational poly-drug users. This study includes 4 phases:

Screening Phase: Subjects will sign informed consent before their entry to the study and completion of all screening procedures. Screening visits should be within 28 days of dosing in Qualification Phase. Subjects who fail screening may not be rescreened.

Qualification Phase: Eligible subjects who meet all inclusion criteria and none of the exclusion criteria will enter a subject- and investigator-blind placebo-controlled, 2-period crossover design Qualification Phase. Subjects will be randomized to a test dose of 1-mg alprazolam and placebo in a crossover manner with a washout period of at least 3 days (72 hours) between each dose. “Drug-liking” response will be assessed before and after alprazolam and placebo administration using a 100-mm bipolar Drug Liking Visual Analog Scale (VAS). Only subjects who meet alprazolam qualification criteria (see Section 6.1.1) will be eligible to enter the Treatment Phase.

Treatment Phase: This will be a subject- and investigator-blind, placebo- and active-controlled, 5-period crossover design. Subjects will be randomized to 1 of 10 dosing sequences; each dosing sequence consists of 5 dosing periods that evaluate the abuse potential of 1 of the 5 study treatments: placebo, 2-mg alprazolam, and 100-mg lasmiditan, 200-mg lasmiditan, and 400-mg lasmiditan. The washout period between each dose should be at least 3 days (72 hours).

Eligible subjects will be admitted to the clinical research unit (CRU) on Day -1 before the planned study drug dosing during each of the dosing periods in both the Qualification Phase and Treatment Phase. After verification of subjects’ eligibility, including a urine drug screen at time of CRU admission, blinded study drug will be administered on Day 1 after an overnight fast. Abuse potential will be assessed using Drug Effects VAS Battery. Adverse events, vital signs, and ECGs will be monitored, and PK samples will be collected according to the Study Schedule (Section 2).

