Prospective approval of protocol deviations to recruitment and enrollment criteria, also known as protocol waivers or exemptions, are not permitted.

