6.2. Exclusion Criteria

Subjects will be excluded from study enrollment if they meet any of the following criteria at screening and/or enrollment:

- [9] are investigative site personnel directly affiliated with this study and their immediate families. Immediate family is defined as a spouse, biological or legal guardian, child, or sibling.
- [10] are Lilly or Covance employees
- [11] are currently enrolled in a clinical study involving an investigational product or any other type of medical research judged not to be scientifically or medically compatible with this study.
- [12] have been dosed with an investigational drug within the 30 days prior to admission during the Qualification Phase.
- [13] have previously completed or withdrawn from this study or any other study investigating lasmiditan, and have previously received the investigational product.
- [14] have known allergies to lasmiditan, alprazolam, related compounds, or any components of the formulation, or a history of significant atopy.

- [15] has evidence of drug or alcohol dependence (excluding nicotine and/or caffeine) within the past 1 year as defined by the *Diagnostic and Statistical Manual of Mental Disorders*, 4th Edition, Text Revision (DSM-IV-TR), or has a lifetime history of participation in a drug rehabilitation program, excluding past participation in tobacco smoking cessation programs or previous court mandated treatment.
- [16] are currently seeking or participating in treatment for addiction or substance-related disorders, or have recovered from substance abuse disorder.
- [17] have a significant history of or current cardiovascular (including arrhythmia, bradycardia, heart block), respiratory, hepatic, renal, gastrointestinal, endocrine, hematological, or neurological disorders capable of significantly altering the absorption, metabolism, or elimination of drugs; of constituting a risk when taking the investigational product; or of interfering with the interpretation of data.
- [18] have a history of significant psychological illness, including any affective disorders within the past year, or are currently taking medications for psychological illness, including selective serotonin reuptake inhibitors, serotonin-norepinephrine reuptake inhibitors, monoamine oxidase inhibitors, or tricyclic antidepressants.
- [19] are currently taking prescription or over-the-counter (OTC) medications other than those that are permitted (as outlined in Section 7.7).

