8.1.1. Discontinuation of Inadvertently Enrolled Subjects

If the sponsor or investigator identifies a subject who did not meet enrollment criteria and was inadvertently enrolled, a discussion must occur between the Lilly clinical pharmacologist or CRP and the investigator to determine if the subject may continue in the study. If both agree it is medically appropriate to continue, the investigator must obtain documented approval from the Lilly clinical pharmacologist or CRP to allow the inadvertently enrolled subject to continue in the study with or without continued treatment with investigational product.

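### Section 3.3 says any prior seizure or depression history excludes because of alprazolam risk, but Section 6.2 does not fully carry this out

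*Protocol*

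**What the plan says.** Protocol Section 3.3 (Benefit–Risk Assessment) acknowledges that "there is no anticipated therapeutic benefit for the subjects in this study" and then describes how risk from alprazolam is contained. One of the protections is exclusion of those at risk from the drug, "including subjects with a prior history of benzodiazepine dependence, seizures, or depression and concomitant use of CYP3A inhibitors will be excluded from the study". The seizure and depression items carry no time window, no severity threshold and no reference to judgement.

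Entry is governed by the lists. Section 5.1 states: "Eligible subjects who meet all inclusion criteria and none of the exclusion criteria will enter" the Qualification Phase. The opening text of Section 6 adds: "Prospective approval of protocol deviations to recruitment and enrollment criteria, also known as protocol waivers or exemptions, are not permitted". Section 6.2 does not refer back to Section 3.3.

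The criterion in Section 6.2 closest to depression is [18], which excludes subjects who "have a history of significant psychological illness, including any affective disorders within the past year, or are currently taking medications for psychological illness". For seizures the closest is [17]: a significant past or current disorder in one of several organ systems, neurological included, that could alter drug handling, pose a risk with the investigational product, or disturb interpretation of the data. None of criteria [9] to [29] mentions seizures or epilepsy.

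**The concern.** A benefit–risk section should describe the protections that are actually applied. Here it describes a stronger one than the criteria list delivers for two histories that the protocol itself links to alprazolam risk. Screening staff who follow Section 6.2 to the letter could admit a subject whom Section 3.3 says is excluded, and that subject would then receive alprazolam without prospect of benefit. Two screeners could also reach opposite decisions on the same history.

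There is a further consequence after enrollment. The documented sponsor–investigator discussion in Section 8.1.1 begins with these words: "If the sponsor or investigator identifies a subject who did not meet enrollment criteria and was inadvertently enrolled". A subject who slips through the gap has met the listed criteria, so that review need not start when the history comes to light.

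**Working it through.** No calculation of error rates or power applies, so the check sets the four items in the Section 3.3 sentence against the criteria that could implement them.

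1. **Benzodiazepine dependence: largely in place.** Criterion [15] has a one-year window for dependence but adds a lifetime bar for drug rehabilitation. Criterion [16] excludes people who have recovered from a substance abuse disorder, without a time limit.
2. **CYP3A inhibitors: in place.** Criterion [27] and Section 7.7 both exclude them.
3. **Depression: partly in place.** Depression is an affective disorder, and the only words in [18] that address affective disorders carry the past-year limit. The medication part of [18] covers current use only. Criterion [28] covers danger to self, or suicidal ideation or behavior in the past 6 months, not past depression as such. The lead phrase of [18], on significant psychological illness, has no time limit and may reach significant older episodes. On that reading, what is left is older depression, off medication and not judged significant. Example: an episode that resolved 18 months ago, untreated since. Section 3.3 excludes this subject; under [18] the answer depends on how the sentence is parsed and on what counts as significant.
4. **Seizures: by judgement only.** Criterion [17] has no time limit. Appendix 1 defines investigational product to include a reference drug, so the risk wording in [17] extends to alprazolam, and Section 3.3 itself identifies seizure history as such a risk. Most seizure histories are therefore covered. What is left is a past seizure not judged a significant neurological history. Criterion [26] concerns brain injury and concussion. Criterion [19] with Section 7.7 bears on current anticonvulsant use, but Section 7.7 also lets stable medication continue, and neither reaches a past seizure with no current treatment. Criterion [29] permits exclusion by opinion but does not require it.

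Count: 4 items in the sentence, 2 implemented (one of them largely), 4 − 2 = 2 not fully implemented.

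Maximum alprazolam exposure of one subject in the gap: 1 mg (Qualification Phase) + 2 mg (Treatment Phase) = 3 mg in 2 single doses. This agrees with Section 3.3: "a maximum of 2 doses within the therapeutic dose range of alprazolam will be administered to minimize potential risks".

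The number of such subjects cannot be computed, because the documents give no prevalence of either history.

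**The case against.** The strongest reply is that the protection exists in substance. An investigator who has read Section 3.3 knows that seizure history is an alprazolam risk, and [17] then excludes a significant history without a time limit. The past-year phrase in [18] can be read as an extension that adds even minor recent affective disorder to an untimed exclusion of significant illness. Criterion [29] allows the investigator or sponsor to exclude anyone thought unsuitable, for either history, at any time and any severity. Inclusion [1] requires overt health as determined from the medical history. If a history emerges later, Section 8.2 allows discontinuation for medical or safety reasons, or by investigator decision, whether or not a criterion was missed. Subjects must also have prior experience with CNS depressants ([7]) and tolerate 1 mg before any 2-mg dose (Section 6.1.1).

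Most of this stands, and it makes the gap small. It does not close it. These routes permit exclusion or depend on a judgement of significance, whereas Section 3.3 promises exclusion outright. Nor is reliance on [17] the protocol's usual practice for related histories: sleep disorder ([22]), vertigo or syncope ([25]) and brain injury ([26]) each have their own line.

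A reader might infer that subjects with seizure histories are generally admissible, or that all depression older than one year is. The documents do not support either: [17] covers most seizure histories, and the untimed part of [18] can cover significant past depression. Nor do they support an inference that such a subject could not be removed once found, given Section 8.2.

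**Conclusion.** Wrong as written, of minor severity: Sections 3.3 and 6.2 contradict each other on a stated safety exclusion. Two narrow groups are affected: people with depression that resolved more than a year ago, off medication and not judged significant, and people with a past seizure not judged significant whom nobody excludes under [29]. The conclusion assumes that Section 3.3 means what it says without qualification and that the Section 6.2 list is the operative rule, as Section 5.1 indicates.

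A reader might go further and infer demonstrated harm or a threat to the trial's conclusions. The documents quantify no added risk from either history at these doses, and dosing is inpatient with monitoring. The mismatch does not touch alpha, power or the primary Drug Liking analysis.

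**What to change.** Amend Section 6.2 in two places:

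- Add a separate criterion excluding a history of seizures at any time.
- In [18], exclude any prior history of depression without the one-year limit. The limit may stay for other affective disorders.

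If the sponsor does intend the one-year window for depression, correct Section 3.3 to say so, so that the protection described is the one applied. With the two criteria in place, a subject later found to have had either history would also fall under Section 8.1.1.

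The cost is amendment wording and some additional screen failures, whose number cannot be derived from the documents. Medical history is already taken at screening, so no new procedure is needed. The planned 60 randomized subjects and 50 completers, and the analysis, stay as they are.
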